Comparison of Local Anesthetic Infusion Pump Versus Depofoam Bupivacaine for Pain Managemen

Date 12/12/2015 ID: 15-1535

Purpose

We propose a randomized controlled study to compare the effectiveness of a localanesthetic continuous infusion pump system versus locally injectable FDA approved DepoFoam bupivacaine (Experal) for postsurgical analgesia in patients undergoing unilateral DIEP free flap reconstruction.

Specific Aims

- Compare the amount of postoperative narcotic use in patients with a localanesthetic continuous infusion pump system, locally injectable liposomal bupivacaine, and a control cohort by recording the type and amount of narcotic use from a patient's medication records.
- 2) Examine the incidence of narcotic-related side effects in the experimental groups as compared to the control cohort by documenting incidents of nausea and vomiting, time to first ambulation, and time to first liquid and solid oral intake.
- 3) Survey patient satisfaction with pain management using a visual analog scale during their hospital stay.

Rationale for the Project

Effective post-surgical pain control in patients undergoing unilateral deep inferior epigastric perforator (DIEP) free flap reconstruction. is critical to patient recovery, and can contribute to faster patient mobilization, shorter hosital stays and reduced health care costs. The admisitration of local anesthetics via wound infiltration is standard of care and an effective practice for postsurgical pain management. However, this method only provides relatively brief analgesia, usually lasting only 12 hours. Other FDA approved delivery systems using an indwelling fusion pump catherter (On–Q pump) are currently being used in our practice and may be used to extend the duration of action of locally adminisisted analgesia by continously infusing anesthetic into the wound. Alternativley, a depot form of bupivicaine has been FDA approved and currently used to deliver a single-dose admistered via wound infiltration for prolonged analgesia by allowing for the diffusion of the drug over an extended period of time. Both of these products are used as standard practice during DIEP free flap reconstructions. However, no studies compare the efficacy of these two methods patients undergoing unilateral DIEP flap reconstructions has been done in a prospective, randomized control manner.

Significance

We would like to compare Clevleland Clinic Foundation's experience with unilateral DIEP flap breast reconstruction to determine if postoperive pain management is improved

with either Depobupivicaine, a local infusion anesthetic pump as comapred to patients given standaad analgesic. We would like to conduct this study to better serve DIEP surgery patients

In a IRB approved pilot study performed by [name], at Henry Ford Medical Center in Detroit, MI in 2014, depoFoam Bupivicaine was compared to Bupivicane alone in patient undergoing breast reconstruction with transverse rectus abdonius muscle (TRAM) or abdominoplasty procedures.

The primary endpoints were postoperative pain as measured by total postoperative morphine or hydromorphone utilization in a patient controlled analgesia (PCA) and pain scores on visual analog scale (VAS). The VAS was measured while the patients were at rest (VAS-R) and after the patient was asked to cough (VAS-C). Morphine usage was tracked by amount dispensed by the PCA pump. Using the medication chart any rescue medications beyond the PCA usage was also recorded. Patients were also interviewed and asked to rate their postoperative pain on a 10-point scale with 0 being no pain and 10 being the most pain. Other variables recorded were incidents of nausea or vomiting, time to first ambulation, and time to first liquid and solid oral intake. All variable measurements were obtained at 30 minutes, 6 hours, 12 hours, 24 hours, 48 hours, and 72 hours postoperatively

A total of twenty patients were randomized into Depofoam bupivacaine group (Exparel, n=15), and continuous infusion pump system (On-Q, n=5) after undergoing abdominoplasty or TRAM flaps. The Exparel group demonstrated higher morphine usage at the 30 minute time point compared to the On-Q group (5.2 mg vs 1.2mg), but a significantly lower volume at all other time points when compared to the On-Q group (6.2 mg vs 16.42 mg at 6 hrs; 5.5 mg vs 14.8 mg at 12 hrs; 5.98 mg vs 14.9 mg at 24 hrs; 5.23 mg vs 11.63 mg at 48 hrs; 2.7 mg vs 12.65 mg at 72 hrs). The VAS scores for the On-Q group were higher at the earlier time points (up to 6 hours) when compared to Exparel group and relatively the same during the remainder of the study (Figure 1 and Figure 2). The remaining variables that were examined revealed that the Exparel group had more nausea and vomiting at earlier time points but that the same group was ambulating, drinking and eating solid food at earlier time points than the On-Q group.

From this pilot study we concluded that with the use of a depot form of bupivicaine (Exparel), more effective postsurgical pain control was achieved in patients undergoing abdominoplasty or TRAM flap reconstruction than those that used an indwelling fusion pump catherters (On–Q pump). Further studies are necessary to enroll more participants undergoing these specific procedures in which this type of post surgical pain control may be most effective.

Our goal in this study is to expand the finding based from our pilot study by observing only those that undergo breast reconstruction with a DIEP flap.

[figure not shown]
[figure not shown]

Figure 2

Subjects in the project

Study participants will include non-pregnant women aged 18 years or older scheduled to have unilateral DIEP flap breast reconstruction. Patients will be required to have an ASA physical status classification of 1, 2, or 3. Patients will be excluded if they have a concurrent or recent medical condition that could interfere with study participation, including history of hepatitis, alcohol/substance abuse, uncontrolled psychiatric disorders, known allergy, or contraindication to amide-type local anesthetics, opioids, or propofol. Patients will also be excluded if they have a body weight of less than 50 kg, have participated in another study involving an investigational medication within the prior 30 days, or are taking analgesics (ie, nonsteroidal anti-inflammatory drugs, acetaminophen, or opioids), antidepressants, or glucocorticoids within the 3 days before surgery.

Describe the control population

Group 3 of our study will compromise the control group for our study. Patients in this arm will receive .25% bupivacaine without epinephrine injected using ultrasound guidance in between the internal oblique and transversus abdominis muscles as well as along incisional lines. This form of local wound infiltration is the current standard of care for post-operative pain management for DIEP reconstructions of the breast.

Support the likelihood of recruiting the number of subjects required

Evidence from our Breast Reconstruction database using data transferred from Epic/Clarity, in 2014 show fifty four unilateral DIEP breast reconstructions were performed and in 2013 sixty six unilateral DIEP breast reconstructions were performed.

Project Design and Protocol

All patients meeting the inclusion criteria will be randomized using a blocked randomization technique, stratifying patients by the timing of the procedure, and it will be employed to allocate patients in equal numbers to each group. The randomization will be created using the plan procedure within SAS software (version 9.3 or higher; Cary, NC).. Patients will be assigned to one of three groups: Group 1 -DepoBupivicaine Injection; Group 2- OnQ catheter placement, and the control Group 3- 0.25 % Bupivicaine injection.

Bupivacaine is a commonly utilized medicaiton for post-operative pain control with a favorable side-effect profile. The dosages of medications given in the study are within safe limits.

The maximum safety dosage of bupivicaine is 2mg/kg with a half life of 3.5 hours. This means a 70kg adult could receive 150mg (.15g). This calculation does not account for the slow release profile of DepoBupivicaine which would increase the maximum safe dose.

The DepoBupivicaine patients (Group 1) will receive an injection of 166mg of DepoBupivicaine diluted in 60mL, the On Q patients (Group 2) will receive an infiltration via an OnQ soaker catheter of 0.25% bupivicaine at 4mL/hour (ie. .01 gram/hour) and 0.25% Bupivicaine patients (Group 3) will receive 2mg/kg of 0.25% of bupivicaine.

Consent

All patients will sign an informed consent that will be presented to them during a preoperative visit with their attending surgeon.

Pre-operative Protocol

No preemptive morphine was given to patients. Patients at high risk for post-operative nausea and vomiting will be given Dexamethasone 4mg and Reglan 10 mg. Anesthesia will be given according to Table 1.

Table 1:

Induction	Propofol	
Intubation (muscle relaxation)	Succinylcholine	
Maintenacnce	Sevoflourane	
Muscle relaxation	Rocuronium	
Analgesia	Fentanyl 2-7 mcg/Kg	
Prophylactic Analgesia	Toradol 30- 60 mg	
Reversal	Glycopirolate + Neostigmine	
Anti-emetic	Zofran 4 mg	

Operative Technique

Surgeons for patients randomized to Group 1(DepoBupivicaine) will be given a schematic for injection of DepoBupivicaine. One 20 cc vial of EXPERAL (266 mg) will be diluted with 60 cc preservative-free normal sterile saline for a total volume of 80 cc. The infiltration technique for the DepoBupivicaine (See Baxter et al, and Hivelin et al) will be 20 cc of injected with a 25-gauge needle on either side of the suture line, (Figure 2 and Figure 3) injected directly into the fascia. The injections will be done in between the internal oblique and transversus abdominus muscles as determined via ultrasound.

Another 20 cc of will be injected on the outside edge of the surgical site where the sensory nerves branch up from the fascia to the skin flap. () The final 20 cc will be injected along the length of the incision where the skin will be anchored down with care to inject the product near the ileoinguinal nerve to ensure appropriate analgesic coverage. Once again, the DepoBupivicaine will be injected directly into the fascia above the muscle layer. All patients will have two closed-suction drains placed at the inferior aspect of the donor site, oriented horizontally and remote from the any infusion catheter..

For patients assigned to the Group 2 (OnQ) the surgeons will be given an instruction sheet with specific placement of catheter (See Bulter et al). All patients in the group will have two ON-Q soaker catheters installed into the abdominal donor site before donor-site closure. The catheters will be inserted through 3-mm stab incisions in the suprapubic area and 3 cm caudal to the donor-site incision. One catheter will be placed directly in the plane between the internal oblique and the transversus abdominus (see Hebbard et al), and the second catheter will be placed subcutaneously, superficial to the anterior rectus sheath along the superior aspect of the donor site (Figure 1). At the conclusion of surgery, a 4-ml/hour infusion 0.25% Bupivicaine % solution will be delivered continuously by the continuous infusion

pump system (2 ml/hour through each catheter). All patients will have two closedsuction drains placed at the inferior aspect of the donor site, oriented horizontally and remote from the any infusion catheters.

Patients assigned to the control Group 3 (0.25 % Bupivicaine) will be given 0.25% bupivacaine without epinephrine. A dose of 2mg/kg will be given. Thus, a 80 kg patient will be given 80 cc of 0.25% Bupivacaine . The infiltration technique for the Maracine will be identical to the EXPERAL injection whereby 20 cc of will injected with a 25-gauge needle on either side of the suture line (Figure 2 and Figure 3) directly into the fascia above the muscle layer. The injections will be done in between internal oblique and transversus abdominus muscles as determined via ultrasound. Another 20 cc of will be injected on the outside edge of the surgical site where the sensory nerves branch up from the fascia to the skin flap (Figure 3). The final 20 cc will be injected along the length of the incision where skin will be anchored down; care will be taken to inject the product near the ileoinguinal nerve to ensure appropriate analgesic coverage (Figure 4). Once again, the 0.25% Bupivacaine will be injected directly into the fascia above the muscle layer. All patients will have two closed-suction drains placed at the inferior aspect of the donor site remote from the any infusion catheters and oriented horizontally.

[figure not shown]

Figure 1. A. OnQ catheter *in vivo* prior to closure of open abdomen (See Haller et al) B. Schematic of OnQ catheter place in a plane above the Tranversus Abdominus (TA) (see Hebbard et al)

[figure not shown]

Figure 2. Injecting bupivacaine into fascia and along incisional lines (C) prior to closure(Baxter et al).

Figure 3 A. Open abdomen prior to closure marking site of injection of either DepoBupivicaine or 0.25 % Bupivicaine (White Arrow) B. Using ultrasound probe in vivo C. Schematic of plane between the Internal Oblique and Transversus Abdominus

Post-operative Protocol

No short-acting analgesics, such as Fentanyl, will be given post-operatively. All patients will receive a narcotic intravenously through a patient-controlled analgesia pump programmed for demand-only mode (no basal rate). The patient-controlled anesthesia will be filled with morphine or hydromorphone (if patient sensitivity to morphine). Oral narcotics will be offered when the patient's diet is advanced as tolerated, typically post-operative day 1. Patients will be encouraged to ambulate on post-operative day 1. The continuous infusion pump catheters will be removed by the surgeon when the pump is empty. Drains will be removed when output is less than 30mL in a consecutive 24 hour period.

Our primary endpoints will be postoperative pain as measured by total postoperative morphine or hydromorphone utilization from a patient controlled anesthesia pump (PCA) and pain scores on visual analog scale (VAS). The VAS will be measured while the patient is at rest (VAS-R) and after the patient is asked to cough (VAS-C). For each patient, the area under the curve (AUC) of the VAS-R will be calculated. Morphine usage will be tracked by patient controlled analgesia (PCA) dispensed. Using the medication chart, any rescue medications beyond the PCA will also be recorded. Patients will be interviewed and asked to rate their postoperative pain on a 10-point scale with 0 being no pain and 10 being the most pain. Another variables recorded will include incidents of nausea or vomiting, time to first ambulation, and time to first liquid and solid oral intake. All measurements for variables were obtained at 6 hrs, 12 hrs, 24 hrs, 48 hrs, 72 hrs. Nursing staff on our designated breast reconstruction floor will be instructed on how to interview patients and collect data for the 6 and 12 hour timepoints. This information will be stored on Epic EMR in a stardard note and nurses will be given a smart text to use in order to appropriately ascertain all information. The 24, 48, and 72 hour time points will be collected by the co-investigators. Any pain medications given by PCA, IV or PO will recorded and converted to morphine as diagramed below:

Drug	Parenteral (mg)	Oral (mg)
Morphine	10	30
Hydromorphone	1.5	7.5
Oxycodone	NA	20
Hydrocodone	NA	30-45
Oxymorphone	1	10
Meperidine	75	300
Codeine	130	200

Equianalgesic Potency Conversion TABLE A

Discuss limitations and difficulties

The limitations of our study include potential confounding pain from the mastectomy site, the subjectivity in patient perception of pain, and differences in patient threshold to request patient- controlled anesthesia and oral narcotics

Provide the tentative schedule for completion

Our schedule for the study will be 6 months continuous enrollment and experimentation from September to February, or until our groups are filled.

Data collection

The data fields will be: Birth date, sex, type of surgery, utilization of mesh, number of mg on PCA, VAS at rest and VAS with cough, number of rescue pain medications given, number of incidents of nausea/vomiting, time to first ambulation, time to first liquid and solid intake post surgery.

Planned Data Analysis

The data will be examined with an analysis of variance (ANOVA) procedure with repeated measures. The design will have one between factor, (group (3), and one within factor, time (6). The analysis will test for a group effect, a time effect and a group by time interaction. We anticipate that the three groups will be comparable at the start. This implies the likelihood of a significant interaction term. If this happens, our primary analysis will focus on the ANOVA for the 72-hour time point. This will show us if a differential effect has occurred. All assumptions of the test will be examined and data transformations or nonparametric methods used if indicated.

We will not be utilizing QHS, rather, one of the plastic surgery residents, [name], will serve as our statistician.

Sample Size Justification

We propose to randomly assign individuals recruited during the recruitment period into 3 equal groups. With three groups this translates to a difference between groups of 5 for total morphine used on day 3 and 0.7 for the VAS. This assumes standard deviations of 4.9 for morphine and 0.7 for VAS. Effects of these sizes represent clinically important differences in the range that we believe will happen.

References:

- Feng LJ. Painless abdominoplasty: the efficacy of combined intercostal and pararectus blocks in reducing postoperative pain and recovery time. Plast Reconstr Surg. 2010 Nov;126(5):1723-32.

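### Group 3's worked example gives 200 mg (2.5 mg/kg) at 80 kg, 25% above both the prescribed 2 mg/kg and the plan's own maximum; the volume should be 64 mL, not 80 cc

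*Combined protocol and SAP*

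**What the plan says.** **Group 3 dose.** The dose paragraph under Project Design and Protocol sets the rule: "Group 3) will receive 2mg/kg of 0.25% of bupivicaine". Operative Technique repeats it and converts it to a volume: "A dose of 2mg/kg will be given. Thus, a 80 kg patient will be given 80 cc of 0.25% Bupivacaine".

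**Limit.** The same dose paragraph states: "The maximum safety dosage of bupivicaine is 2mg/kg with a half life of 3.5 hours". It illustrates this with 150 mg for a 70 kg adult. It adds that slow release would raise the ceiling for the depot product. Just before this, the plan gives a general assurance: "The dosages of medications given in the study are within safe limits".

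**Group 3 technique.** After the 80 kg example comes: "The infiltration technique for the Maracine will be identical to the EXPERAL injection whereby 20 cc of will injected". The text places 20 cc on either side of the suture line, a further 20 cc at the outer edge of the site, and a last 20 cc along the incision. It does not say how these portions change with weight.

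**Group 1.** The dose paragraph says these patients "will receive an injection of 166mg of DepoBupivicaine diluted in 60mL". Operative Technique says: "One 20 cc vial of EXPERAL (266 mg) will be diluted with 60 cc", with "normal sterile saline for a total volume of 80 cc".

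**The concern.** The 80 kg example is the only place where the plan turns Group 3's mg/kg dose into a volume, so it is the line a surgeon is likely to follow. It does not agree with the rule it is meant to illustrate. Group 3 is dosed exactly at the plan's stated maximum, so there is no margin to absorb a volume error: any excess over the prescribed dose also exceeds the limit. The plan's allowance for slow release does not help, because Group 3 receives plain bupivacaine.

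The surrounding text makes the slip harder to notice. The technique is called the same as Group 1's, and Group 1's total volume is also 80 cc, so the two figures seem to confirm each other. Group 3 is also the comparator: a surgeon who works from the rule and one who works from the example would give different control doses.

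**Working it through.** **Inputs**
- Group 3 rule: 2 mg/kg of 0.25% bupivacaine (dose paragraph and Operative Technique).
- Group 3 example: 80 kg, 80 cc (Operative Technique).
- Stated maximum: 2 mg/kg (dose paragraph).
- Concentration: the dose paragraph equates 4 mL/hour of 0.25% with 0.01 g/hour. 10 mg / 4 mL = 2.5 mg/mL.

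**Trying to reproduce the plan's 80 cc**

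Volume = (mg/kg × kg) / (mg/mL) = (2 × 80) / 2.5 = 160 / 2.5 = 64 mL. The plan's figure does not reproduce.

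What 80 cc delivers: 80 × 2.5 = 200 mg; 200 / 80 = 2.5 mg/kg. Excess: 200 − 160 = 40 mg; 200 / 160 = 1.25, or 25%.

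Conditions under which 80 cc would be right:
- a patient of 200 / 2 = 100 kg; or
- at 80 kg, a solution of 160 / 80 = 2.0 mg/mL, which is 0.2%.

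The plan states neither.

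**The 20 cc portions**

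The text can be read in two ways:

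| Reading of the first portion | Total | Dose at 2.5 mg/mL | Exceeds 2 mg/kg if unscaled and weight is below |
|---|---|---|---|
| 20 cc on each side | 20 + 20 + 20 + 20 = 80 cc | 200 mg | 200 / 2 = 100 kg |
| 20 cc shared by both sides | 20 + 20 + 20 = 60 cc | 150 mg | 150 / 2 = 75 kg |

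The first reading matches Group 1's 80 cc total. If the example is instead generalised as 1 mL/kg, the dose is 2.5 mg/kg at every weight.

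**Correct rule in volume:** 2 / 2.5 = 0.8 mL/kg. That is 40 mL at 50 kg, 56 mL at 70 kg, 64 mL at 80 kg and 80 mL at 100 kg.

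**Secondary items**
- 70 kg limit: 2 × 70 = 140 mg, not 150 mg. 150 / 70 = 2.14 mg/kg; 150 / 140 = 1.07.
- Group 1: 266 − 166 = 100 mg; 266 / 166 = 1.60.

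**The case against.** The best defence is that the mg/kg rule governs and the example only illustrates it. The rule is stated twice for Group 3, and a surgeon or pharmacist could compute 64 mL from it. That shows which figure to correct. It does not make the example harmless, because the example is a written dosing instruction and nothing elsewhere in the document overrides it.

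Three other objections limit how far the point goes, and they stand.

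- **Fixed 80 cc in light patients.** A reader might infer that a 50 kg patient, the lowest weight admitted, would receive 200 / 50 = 4.0 mg/kg. That needs a fixed 80 cc at every weight, which conflicts with the weight-based rule, and it needs the each-side reading of the first portion. The text gives 80 cc only for 80 kg. The supported excess is 25%.
- **Group 1.** A reader might infer that the depot regimen is undefined, or that 166 mg is incompatible with the operative mixture. Neither follows. The operative text is complete on its own. The 60 mL in the dose paragraph may simply be the same 60 cc of diluent. And 50 cc of the 80 cc mixture would hold 266 × 50 / 80 = 166 mg, although no 50 cc injection is directed. One differing digit remains, possibly a typing error.
- **Toxicity.** The 2 mg/kg ceiling is the plan's own and carries no citation there. The documents show a breach of that ceiling, not clinical harm.

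**Conclusion.** The point holds and must be fixed. At 80 kg the Group 3 example delivers 200 mg against 160 mg prescribed: 40 mg, or 25%, above both the dose rule and the plan's stated maximum. For this arm the example contradicts the assurance that doses are within safe limits. The 2 mg/kg rule itself sits at the maximum, not above it; the breach comes from the example.

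The conclusion rests on two things: the 2.5 mg/mL concentration, which the plan's own conversion supplies, and treating the twice-stated mg/kg rule as the intended one.

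The missing scaling of the 20 cc portions is a real gap, but its size is conditional. Given unscaled, the portions would exceed 2 mg/kg below 100 kg or below 75 kg, depending on the reading. The documents do not say they are to be given unscaled.

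The 166 mg against 266 mg mismatch and the 150 mg limit example are secondary. The limit example sets no arm's dose, and no breach is shown for Group 1 or Group 2.

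**What to change.** **Operative Technique, Group 3**
- Change 80 cc to 64 mL (160 mg) for the 80 kg patient.
- State the total volume as 0.8 mL/kg of 0.25% bupivacaine.
- Say that the injection sites match Group 1 but the portions are scaled to that total, for example in the same proportions, and say whether the first portion is per side or shared between sides.

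**Dose paragraph, Project Design and Protocol**
- Make the Group 1 dose agree with the operative text: 266 mg in a total of 80 cc, if that is what is intended, in place of 166 mg in 60 mL.
- Correct the 70 kg limit example to 140 mg (0.14 g).

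**Cost.** This is a short amendment with no effect on sample size. If enrolment has begun, the Group 3 correction should go out at once.

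The real downside is that Group 3's injected volume will differ from Group 1's 80 cc at every weight except 100 kg (for instance 40 mL at 50 kg and 64 mL at 80 kg), so the two injection arms are no longer matched on volume. Keeping 80 cc at 80 kg within the limit would need a 0.2% solution, which is no longer the 0.25% control that the plan describes as standard care.

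### The Group 3 worked example gives 25% more bupivacaine than the plan's own 2 mg/kg dose and maximum, and Group 1 has two conflicting Exparel doses (166 mg and 266 mg)

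*Combined protocol and SAP*

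**What the plan says.** **Group 3 (plain bupivacaine).** The dosing paragraphs under Project Design and Protocol set the ceiling: "The maximum safety dosage of bupivicaine is 2mg/kg with a half life of 3.5 hours". They illustrate it for a 70 kg adult as 150 mg, and assign Group 3 2 mg/kg of the 0.25% solution. Operative Technique repeats the rule ("A dose of 2mg/kg will be given") and at once converts it: "Thus, a 80 kg patient will be given 80 cc of 0.25% Bupivacaine". It then describes the infiltration as "identical to the EXPERAL injection whereby 20 cc of will injected with a 25-gauge needle on either side of the suture line", followed by two further 20 cc portions. None of the portions is tied to body weight.

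**Group 1 (Exparel).** The dosing paragraph says these patients "will receive an injection of 166mg of DepoBupivicaine diluted in 60mL". Operative Technique instead takes one 20 cc vial containing 266 mg and adds 60 cc of saline, making 80 cc. On the ceiling, the plan says of the depot form: "This calculation does not account for the slow release profile of DepoBupivicaine which would increase the maximum safe dose".

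Project Design and Protocol also states that the study doses are within safe limits. Subjects in the project excludes patients weighing under 50 kg.

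**The concern.** The Group 3 example is the only conversion from mg/kg to mL given for that arm, and it sits in the operative instructions. The intended dose already equals the plan's maximum, so any upward slip goes over it. A surgeon who follows the example exceeds the limit that the plan sets, despite its statement that doses are safe.

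In Group 1 the Exparel dose is the treatment under test. Two surgeons working from different paragraphs would give different doses within one arm, and the trial could not say which dose it had evaluated. The fields listed under Data collection include neither body weight nor the local anesthetic dose given, so the dataset as listed would not show who received what. Opioid use and pain scores, the primary endpoints, could be affected in both arms.

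**Working it through.** **Concentration.** The Group 2 infusion is given as "0.25% bupivicaine at 4mL/hour (ie. .01 gram/hour". That is 10 mg in 4 mL, or 2.5 mg/mL, so the plan itself confirms the strength of the 0.25% solution.

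**Trying to reproduce the 80 cc at 80 kg.**
- Intended dose: 2 mg/kg × 80 kg = 160 mg.
- Volume: 160 mg ÷ 2.5 mg/mL = 64 mL. The plan's 80 cc is not reproduced.
- What 80 cc delivers: 80 mL × 2.5 mg/mL = 200 mg, and 200 ÷ 80 = 2.5 mg/kg.
- Excess: 200 ÷ 160 = 1.25, that is 40 mg or 16 mL too much.
- 80 cc would be right only for a 2 mg/mL (0.2%) solution, a 2.5 mg/kg dose, or a 100 kg patient. The plan states none of these.

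**General rule.** 2 mg/kg ÷ 2.5 mg/mL = 0.8 mL/kg. If a surgeon read the example as 1 mL/kg (an extrapolation; the plan does not state it), the dose would be 2.5 mg/kg at every weight.

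**If the 20 cc portions were given unscaled.** Counting 20 cc on each side of the suture line plus two further portions gives 80 cc (200 mg). Counting 20 cc for both sides together gives 60 cc (150 mg). Both cases assume a fixed volume despite the 2 mg/kg rule.

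| Weight | 2 mg/kg | Correct volume | Fixed 80 cc | Fixed 60 cc |
|---|---|---|---|---|
| 50 kg | 100 mg | 40 mL | 4.00 mg/kg | 3.00 mg/kg |
| 70 kg | 140 mg | 56 mL | 2.86 mg/kg | 2.14 mg/kg |
| 80 kg | 160 mg | 64 mL | 2.50 mg/kg | 1.88 mg/kg |
| 100 kg | 200 mg | 80 mL | 2.00 mg/kg | 1.50 mg/kg |

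A fixed 80 cc exceeds 2 mg/kg below 200 ÷ 2 = 100 kg. A fixed 60 cc exceeds it below 150 ÷ 2 = 75 kg.

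**Illustrated maximum at 70 kg.** 2 × 70 = 140 mg, against the stated 150 mg; 150 ÷ 140 = 1.07, about 7% high. This figure sets no arm's dose.

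**Group 1.**
- Dose ratio: 266 ÷ 166 = 1.60, a difference of 100 mg.
- Concentration from Operative Technique: 266 mg ÷ 80 mL = 3.33 mg/mL.
- Concentration from the dosing paragraph: 166 ÷ 60 = 2.77 mg/mL if 60 mL is the final volume, or 166 ÷ 80 = 2.08 mg/mL if 60 mL is diluent added to the 20 cc vial.

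On the second reading the volumes agree, but the doses do not agree on either.

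**The case against.** The arithmetic is not in dispute; the case against concerns weight and scope. The 2 mg/kg rule is stated correctly twice, and only its illustration is wrong. A careful clinician could work out 64 mL. The larger excesses, up to 4.0 mg/kg at 50 kg, need a fixed volume that contradicts the stated rule. That is fair: they are conditional, and the firm error is 25% at 80 kg.

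For Group 1, only Operative Technique is a recipe that can be carried out. At the vial strength (266 mg in 20 cc, or 13.3 mg/mL), 166 mg would need about 12.5 cc, and nothing tells a surgeon to use part of a vial. A one-digit typing error is a plausible explanation. This makes actual use of 166 mg less likely, but the text does not settle which dose is meant.

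Scaling Group 3 by weight also gives it a smaller volume than Group 1's 80 cc at most weights, although the technique is described as identical. This is true, but the difference already follows from the plan's own rule of 2 mg/kg of a 0.25% solution. Finally, an injection schematic is mentioned for Group 1 only, and its contents are not shown, so it cannot be assumed to carry the error.

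**Conclusion.** The concern holds. The Group 3 example exceeds the plan's stated dose and maximum by 25%, using only the plan's own figures. Group 1 carries two doses that differ 1.60-fold, with no statement of which governs. These are errors in the instructions that define the arms, so they must be corrected before the plan is used.

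The conclusion rests on no outside figure. It does not claim clinical toxicity, and it does not claim that Exparel exceeds the ceiling. The fixed-volume figures hold only if the portions are given unscaled.

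**What to change.** **Group 3.** Change the 80 kg example to 64 mL and state the dose as 2 mg/kg, equal to 0.8 mL/kg of 0.25% solution. Scale the portions to that total. With four equal portions each is 0.2 mL/kg: 16 mL at 80 kg, 14 mL at 70 kg, 10 mL at 50 kg. If the investigators want volumes matched to Group 1, they could make the 2 mg/kg dose up to 80 cc with saline for patients up to 100 kg, but the solution would then be weaker than 0.25% below that weight (160 mg ÷ 80 mL = 2 mg/mL at 80 kg) and the plan would have to say so.

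**Illustrated maximum.** Change 150 mg to 140 mg at 70 kg.

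**Group 1.** State one dose in mg and one final volume, in the same words in the dosing paragraph and Operative Technique. The investigators and pharmacy should confirm which; 266 mg in 80 cc is the more complete recipe.

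**Related text.** Check the surgeon schematic and revise it where needed, and recheck the statement that doses are within safe limits against the corrected figures.

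The cost is a protocol wording correction and, where needed, a revised schematic. Sample size and analysis do not change.
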